3. STUDY SUMMARY

Full study title	The Impact of Type 2 Diabetes and Exercise on Liver Fat Quality
Internal ref. no. (or short title)	Diabetes, Exercise & Liver Fat (DELIVER)
Study Design	Part A: cross-sectional study Part B: randomised controlled trial (RCT)
Scientific abstract	
Non-alcoholic fatty liver disease (NAFLD) is characterised by an excessive accumulation of liver fat which is intricately linked to type 2 diabetes (T2DM), cardiovascular and renal disease. Recent research suggests that liver fat quality i.e. the composition of fat stored in the liver (saturated, unsaturated, polyunsaturated), may represent a key link between excess liver fat and adverse metabolic health outcomes. The proposed research contains a cross-sectional component (Part A) that will explore whether liver fat quality differs in male NAFLD patients with ($n = 26$) or without T2DM ($n = 14$); and a randomised controlled trial (Part B) (one exercise training and one control group) that will determine if exercise (150 - 200 min per week, 6 weeks) can beneficially modify liver fat quality in NAFLD patients with T2DM/prediabetes ($n = 26$, 13 per group). Liver fat quality will be assessed in both studies via magnetic resonance (3T) spectroscopy ($^1\text{H-MRS}$) using validated methods. This research will investigate whether liver fat quality is a novel therapeutic target for T2DM patients with NAFLD and determine whether exercise is able to favourably modify liver fat quality.

Study Participants	
Part A (cross-sectional study): 14 obese men with non-alcoholic fatty liver disease (NAFLD) and 26 obese men with NAFLD and T2DM
 
Part B (RCT): 26 obese men with NAFLD and T2DM/prediabetes

Planned Study Period	1 st September 2018 to 31 st December 2022 (52 months)

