9. STUDY DESIGN

Summary of trial design

This study consists of two parts: a cross-sectional component (Part A) and a randomised controlled trial (RCT) (Part B). All participants will complete Part A (non-diabetic obese men with NAFLD and obese men with NAFLD & T2DM/prediabetes); however, only one of the two study groups will progress to Part B (obese men with NAFLD and T2DM/prediabetes) (see Figure 1).

All prospective study participants will undergo a telephone interview in order to verbally assess potential study eligibility. This conversation will be conducted by a member of the study team and is anticipated to last up to 30 minutes. Participants wishing to take part and who appear eligible will subsequently be invited to attend the first face-to-face study assessment visit (visit one).

Study assessment visit one will occur at the Sir Peter Mansfield Imaging Centre located on the University of Nottingham Campus. Written informed consent shall be obtained at the beginning of this visit. After this, several questionnaires relating to health status and lifestyle habits will be completed before anthropometric measurements are taken. Participants will then undergo an MRI scan of the liver and abdominal region. Before participants leave the centre they shall be familiarised with a wrist worn (watch-like) physical activity monitor that they will wear continuously for the next seven days; and a food diary that they will complete on two week and one weekend day.

Participants will be invited to attend a second assessment visit if their MRI scan shows that they meet the criteria for clinically elevated liver fat ($> 5.56\%$). Visit two will take place at the Queens Medical Centre Hospital (Nottingham) or the Leicester General Hospital (depending on participant preference). During this session a fasting blood sample will be taken and a healthcare professional will perform a medical exam that will include an ECG. Finally, participants will complete a symptom limited peak oxygen uptake test on a treadmill. Vital signs will be monitored throughout this test by a healthcare professional.

Participants' involvement in this study will end after visit two for those only taking part in Part A. At this point, participants destined to progress to Part B of the study will be randomised to one of two six week interventions (1:1) (exercise training or control) by the trial statistician. Participants will be notified of their assignment by telephone.

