contacted via telephone – depending on the preference of the investigator who is responsible for curating the participant database.

Community and internet

Participants will be recruited from the general public through various routes:

- *Commercial weight management programmes*: session leaders from local weight loss programs will advertise the study to their cohorts by mentioning the study at meetings and providing copies of Participant Information Leaflets / Sheets.
- *Websites*: the study will be advertised on University (Loughborough, Nottingham and Leicester) and Hospital Trust (Nottingham, Leicester) websites where links to investigator contact details and electronic versions of study information resources will be provided. Anyone interested in taking part will subsequently be able to contact the research team.
- *Local media*: the research team will liaise with University (Loughborough, Nottingham and Leicester) public relations teams to advertise the study within the community. Advertisements routes may include press releases (website, radio, newspaper) where investigator's contact details will be provided for anyone who may be interested in taking part after hearing about the study.
- *Study posters*: will be displayed in hospital trusts, university and local community (where permitted).

Inclusion criteria

- Men
- $\geq 30 - \leq 75$ years of age
- Body mass index $\geq 27 - \leq 45$ kg/m² (or ≥ 23 to 45 kg/m² if south Asian)
- Waist circumference ≥ 94 cm (or ≥ 90 cm if south Asian)
- Clinically elevated liver fat ($\geq 5.56\%$ assessed via ¹H-MRS)[17]
- Participant is willing and able to give informed consent to participate
- Participant can communicate effectively in English
- Participant is able to meet the time demands of the study

Additional criteria for participants without T2DM

- HbA1c $< 6\%$

Additional criteria for participants with T2DM/prediabetes

- Diagnosed T2DM or prediabetes

- Treatment via lifestyle or metformin only within the last 6 months
- HbA1c 6.0 – 10%
- Willingness to enter Part B of the study and be randomised to exercise training or control
- Able to meet the time and physical demands encompassed within the exercise training intervention

Exclusion criteria

- Contraindications to magnetic resonance procedures
- Contraindications to exercisetraining
- Participating in regular purposeful exercise training of vigorous intensity – frequency ≥ 3 sessions per week and intensity ≥ 6.0 metabolic equivalents (METs)

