12. TREATMENT OF TRIAL PARTICIPANTS

Overview of procedures

This study will consist of two parts (A and B) and will include two discrete groups of participants.

1. Obese men with NAFLD – will complete Part A only
2. Obese men with NAFLD and T2DM/prediabetes – will complete Part A and B

Table 1 provides an overview of the procedures that participants will undertake as part of this study.

Table 1: summary of trial procedures for study participants

Visit	Duration	Procedure(s)
Study Part A – all participants		
Telephone interview	30 min	Verbal eligibility check against inclusion / exclusion criteria
Assessment visit 1 (SPMIC)	2 h	Informed consent, study questionnaires, anthropometry, blood pressure, finger prick test, MRI scan
Assessment visit 2 (QMC or LGH)	2 h	Fasting blood sample, medical examination, peak oxygen uptake test
Study Part B – obese men with NAFLD & T2DM/prediabetes only		
3-20 Exercise training (supervised sessions at QMC, LGH or Loughborough University)	1 h per session	Heart rate, RPE
Assessment visit 3 (SPMIC)	2 h	Study questionnaires, anthropometry, blood pressure, MRI
Assessment visit 4 (QMC or LGH)	2 h	Fasting blood sample, peak oxygen uptake test

RPE - ratings of perceived exertion, MRI magnetic resonance imaging, HbA1c – glycated haemoglobin, SPMIC – Sir Peter Mansfield Imaging Centre, QMC – Queens Medical Centre Hospital, LGH - Leicester General Hospital

At the beginning of the study, all potential participants will complete a telephone interview to verbally assess eligibility for the study (age, sex, activity status, smoking status, habitual alcohol intake,

understanding of English, medical history, medication use, contraindications to the study procedures, willingness and ability to undertake six weeks exercise training). Participants who are potentially eligible will then be invited to attend the Sir Peter Mansfield Imaging Centre located on the University of Nottingham campus for the first study assessment visit.

Prior to each visit to a study site (including assessment visits and supervised training sessions) participants will be contacted via telephone by a member of the research team within 72 hours of their visit to complete a site-specific COVID-19 symptom screening questionnaire. Upon arrival at the study site, participants will verbally complete the COVID-19 symptom screening questionnaire again with a member of the research team.

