The assumptions associated with each model will be assessed and where these are not met alternative models or parameterisations will be considered. A value of $P < 0.05$ will be considered statistically significant for all analyses. Statistical analyses of the baseline data and all future analysis will be carried out using STATA version 15.

The Number of Participants

The sample size for the research outlined in this protocol was undertaken by a statistician in the Leicester Clinical Trials Unit. The sample size calculations were informed by data published in a previous study which validated the method for measuring hepatic fat quality via ¹H-MRS[16].

Part A of this research (cross-sectional analyses) was powered (80%) to detect a difference in the liver saturated fat indices of 0.5 between men with NAFLD with T2DM versus non-diabetic men with NAFLD (alpha 5%, SD 0.4 in each group). 28 participants are needed to provide adequate statistical power for this analysis (14 in each group). Based on the same data, the power calculation showed that 24 participants are needed for Part B of the outlined research (RCT). This is inflated to 26 to allow for expected drop-out (10%).

Please note that the baseline data for all participants entering Part B of this research will be used in Part A and therefore the cross-sectional analyses will include data from 26 men with NAFLD & T2DM and 14 non-diabetic men with NAFLD.

Procedure for dealing with missing and spurious data

Missing data will be replaced using multiple imputation or another appropriate method. In Part B, participants completing less than 85% of all training sessions will not be included in the final analysis.

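### The Part A co-primary is defined, interpreted and powered as T2DM versus no T2DM, but the group analysed is T2DM or prediabetes

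*Protocol*

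**What the plan says.** Wherever the protocol defines the Part A contrast, it names T2DM alone. This holds for the aims and Study Participants entry (section 3), co-primary objective (a) and the matching secondary objective (section 8), co-primary outcome 1 (section 9), and the t-test groups and the diabetic versus non-diabetic logistic outcome (section 14). Section 3 lists "14 obese men with non-alcoholic fatty liver disease (NAFLD) and 26 obese men with NAFLD and T2DM" for Part A. The sample size text is powered for a "difference in the liver saturated fat indices of 0.5 between men with NAFLD with T2DM versus non-diabetic men with NAFLD", and then says that "the cross-sectional analyses will include data from 26 men with NAFLD & T2DM and 14 non-diabetic men with NAFLD".

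Wherever the protocol says who enters Part A, the group is wider:

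- Section 9: "All participants will complete Part A (non-diabetic obese men with NAFLD and obese men with NAFLD & T2DM/prediabetes".
- Section 10: the group must have "Diagnosed T2DM or prediabetes", with HbA1c 6.0 to 10%. The comparator must have HbA1c below 6%.
- Section 12: Parts A and B "will include two discrete groups of participants", the second being "Obese men with NAFLD and T2DM/prediabetes – will complete Part A and B".
- Section 14: "the baseline data for all participants entering Part B of this research will be used in Part A".

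No section limits Part A to men with T2DM or handles prediabetic men separately in its analysis.

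**The concern.** The Part B wording names T2DM/prediabetes; the Part A wording does not, although both parts use the same 26 men. Section 3 describes these men one way for Part A and the other way for Part B, and section 14 does the same in its description of the methods.

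A man with prediabetes does not have T2DM. Under an objective that compares men with and without T2DM he does not belong in the T2DM group, yet the t-test would count him there and the logistic model would code him as diabetic. At stake is what a co-primary result means: section 3 says the study seeks the impact of T2DM on liver fat quality, and a mixed group does not estimate that. The assumed difference and the power are also stated only for the narrower contrast.

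**Working it through.** **Inputs (section 14).** Difference 0.5, SD 0.4 in each group, alpha 5%, 80% power, 14 per group needed, 26 v 14 planned. Alpha is taken as two-sided, which the protocol does not state. The protocol gives neither the expected share of prediabetic men nor their saturated fat index.

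**The plan's own figure.** Power comes from the noncentral t with n₁+n₂−2 degrees of freedom and noncentrality Δ / (σ√(1/n₁+1/n₂)). With Δ = 0.5 and σ = 0.4, 12 per group gives 0.833 (11 gives 0.796), so 24 men suffice. That matches the Part B figure. The stated 14 per group for Part A gives 0.889, not 0.80. The 28 is therefore conservative and does not affect this point.

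**T2DM men only, against 14.** For 26 men, √(1/26+1/14) = 0.3315, so the noncentrality is 0.5/(0.4×0.3315) = 3.77 on 38 df. The 95% CI half-width is t(0.975, n+12)×0.4×√(1/n+1/14).

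| T2DM men | Power at 0.5 | 95% CI half-width |
|---|---|---|
| 26 | 0.957 | ±0.27 |
| 14 | 0.889 | ±0.31 |
| 10 | 0.823 | ±0.34 |
| 9 | 0.797 | ±0.36 |
| 6 | 0.678 | ±0.41 |

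**Room for dilution at 26 v 14.** The smallest difference with 80% power is 0.381. Relative to 0.5 that is 1 − 0.381/0.5 = 24%. This ignores the small extra variance from mixing.

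**What the mixed t-test estimates.** Let p be the prediabetic share of the 26 and f the fraction of the T2DM difference present in prediabetic men. The expected difference is 0.5×(1 − p(1−f)). The variance in the mixed group is 0.16 + p(1−p)(0.5(1−f))², pooled with 0.16 in the comparator. Both p and f are assumptions, so a range is shown. Each cell gives the difference, then the power at 26 v 14.

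| p | f = 1 | f = 0.5 | f = 0 |
|---|---|---|---|
| 25% | 0.50, 0.957 | 0.44, 0.881 | 0.375, 0.714 |
| 50% | 0.50, 0.957 | 0.375, 0.762 | 0.25, 0.374 |
| 75% | 0.50, 0.957 | 0.31, 0.612 | 0.125, 0.134 |

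Worked case, p = 0.5 and f = 0.5:

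- Difference: 0.5×(1 − 0.25) = 0.375.
- Mixed-group variance: 0.16 + 0.25×0.0625 = 0.1756.
- Pooled variance: (25×0.1756 + 13×0.16)/38 = 0.1703.
- Power: 0.762 (simulation 0.766).

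Restricting this case to its T2DM men (13 v 14) gives 0.877. With p = 0.5 and f = 0.75 the difference is 0.4375 and power is 0.891.

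**The case against.** The strongest reply is that this is a wording conflict. The HbA1c ranges do not overlap, all Part B entrants go into Part A and the test is fixed, so no analyst would be unsure whom to include. That is right about the data set. It does not settle what the result may be called, and here the wording defines the quantity that a co-primary claims to estimate.

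Second, 0.5 has no documented basis as a T2DM difference. Section 14 attributes the inputs to the study that validated the spectroscopy method. Section 7 describes that study's comparison as people with and without elevated liver fat, and mentions no diabetes contrast. The reference number given in section 14 leads to an exercise trial. This stands as a caution: the 24% margin is relative to a figure that the protocol labels as T2DM but does not show to be one. The label is still the protocol's own.

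Third, the mixed-group powers rest on an assumed share and an assumed effect. That is so. They show a range and establish no loss.

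Fourth, diabetes status may not be recorded as an analysis variable, and HbA1c alone need not separate metformin-treated T2DM from prediabetes. In part this stands. Diagnosis is an eligibility item, and section 11 collects medical history, current medication and laboratory HbA1c, so the information should exist. The data set must carry it explicitly.

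Finally, a supporting T2DM-only comparison could sit in an analysis plan that is not shown. Its absence is not the defect. The defect is that the protocol states two incompatible populations for one co-primary.

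**Conclusion.** The concern holds. The current text gives the Part A co-primary a T2DM contrast and fills it with a T2DM/prediabetes group. The firm consequence needs only one condition, that at least one prediabetic man is enrolled: the t-test then does not estimate the stated contrast, and a T2DM conclusion drawn from it would be mislabelled.

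The effect on power is uncertain. There is no loss if prediabetic men carry the full 0.5. At 26 v 14, power stays at 80% or more while the mixed difference is at least about 0.38. It falls to 0.76 if half the men are prediabetic with half the difference. These figures assume a two-sided 5% t-test, SD 0.4 within each subgroup, and the protocol's 0.5 for T2DM. The point should be fixed before analysis, and the data remain usable.

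**What to change.** Reconcile the Part A wording with the group analysed, before any Part A comparison is run, in one of two ways.

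1. **Relabel.** Change the Part A objectives, co-primary outcome 1, the t-test groups, the logistic outcome, the description of the 26 men and the power statement to T2DM/prediabetes versus men with HbA1c below 6%. Say in the power statement that 0.5 was set for T2DM versus non-diabetic men, so that the calculation is not read as having been made for the wider group. Base any conclusion about T2DM on a supporting T2DM-only comparison.
2. **Restrict.** Keep T2DM versus non-diabetic as the co-primary, limit it to men with T2DM, and restate power for their number from the first table above.

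Either way, record T2DM or prediabetes for each man as a variable, from the diagnosis at eligibility, checked against the history, medication and laboratory HbA1c already collected.

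The cost is wording in sections 3, 8, 9 and 14, with no new visits or tests. Under the first option the co-primary no longer speaks to T2DM alone. Under the second, prediabetic men leave the co-primary, and fewer than the 14 T2DM men that section 14 asks for may remain; power is below 80% with 9 or fewer.

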Participants will be asked to attend the second study assessment visit having not eaten since the prior evening. These visits will therefore occur in the morning (before 10:30). At the start of this visit participants will provide a fasting venepuncture blood sample (50 mL blood) after having sat down for 10 minutes. This sample will be collected from an antecubital vein by an individual trained and experienced in phlebotomy. One blood bottle will be sent to hospital pathology labs for the analysis of glycated haemoglobin. The remaining samples will be processed immediately and stored until the end of the trial within -80°C freezers at the research sites. Following the last participants visit, samples will

be transported to Loughborough University (at -80°C) by a commercial courier. Samples will then be analysed in batch for:

- Lipids
- C-reactive protein
- Liver enzymes
- Glucose
- Insulin
- Nonesterified fatty acids
- Hepatokines
- Inflammatory proteins
- Genotype (gene variants linked to NAFLD)

Medical evaluation and aerobic fitness

A healthcare professional will take a full medical history from participants in order to identify any factors that may prohibit individuals from completing the study. Blood pressure will be measured, and a 12 lead ECG and a physical examination* will also be performed. Finally, a symptom limited progressive treadmill exercise test will be undertaken on a treadmill. This test will require participants to exercise at increasingly harder intensities until volitional exhaustion. A clinical professional will monitor participants' blood pressure and ECG during this test which will be terminated if clinically indicated.

* The physical examination is optional and dependent on findings from Medical History and 12 Lead ECG. It is to be performed by individuals qualified to do physical examinations.

Randomisation

After visit two, participants entering Part B of the study will be randomised (1:1) to condition (exercise training or control). Randomisation will be performed by the trial statistician ([name]) (see section 13 for additional details). The involvement of participants who are only completing Part A of the study will end at this point.

Six week intervention

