Participants randomised to control will receive no interventions during the six-week intervention phase. During this time, control participants will be asked to not change any aspects of their lifestyles. Ahead of week five, participants will be posted a physical activity monitor to wear continuously during week five and six. Participants will also complete weighed food diaries during week five (two weekdays and one weekend day).

Participants randomised to exercise training will complete four exercise training sessions per week during the six-week intervention. Each week, at least one session will be supervised by the research team whilst the remaining sessions will consist of participants undertaking brisk walking on their own. All exercise sessions will be composed of continuous moderate-intensity exercise and last 35 - 50 minutes in duration (depending on intervention week). The specific details relating to these training sessions can be seen in section 12 (Table 2).

Assessment visit 3 (post-intervention) - Sir Peter Mansfield Imaging Centre (University of Nottingham)

The assessments undertaken at visit three will be a repeat of those completed during visit one.

Assessment visit 4 (post-intervention) - Leicester General Hospital (Leicester Diabetes Centre) or Queens Medical Centre Hospital (NIHR Nottingham BRC)

The assessments undertaken at visit four will be a repeat of those completed during visit two except that a medical examination will not be performed.

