Participants progressing to Part B of the study (obese men with NAFLD and T2DM/prediabetes) will then be randomised to exercise training or control for six weeks. Participants will be made aware of their group assignment via telephone. Control participants will undergo no interventions and will be asked not to alter any aspect of their lifestyle during the next six weeks. Ahead of week five, control participants will receive a physical activity monitor and food diary in the post to enable them to record their habitual physical activity and food intake during weeks five and six. After the intervention phase has ended, control participants will complete two additional study assessment visits (visits three and four) to obtain post-intervention measurements. These visits will be a repeat of assessment visits one and two (excluding the pre-exercise screening in visit two).

Participants randomised to the exercise training group will complete 24 exercise training sessions (35 to 50 min of moderate-intensity exercise) during the six-week intervention. Four training sessions will be completed each week, with at least one of these sessions being supervised by the study team. Participants will have the option to undergo these sessions at Loughborough University (National Centre of Sport and Exercise Medicine), Nottingham (Queens Medical Centre Hospital) or Leicester (Leicester General Hospital) depending on preference. The remainder of the sessions each week to be completed by participants will be unsupervised sessions of brisk walking which will be recorded via a heart rate monitor and watch. Participants will be supported after each unsupervised session via a telephone call from a member of the research team and the intensity and duration of the session will be recorded from the watch. Participants in the exercise group will wear a wrist-worn movement sensor throughout the entire training phase and will complete weighed food diaries (two week and one weekend day) in the fifth and sixth weeks of training.

Exercise training

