14. STATISTICS

Description of statistical methods

Descriptive statistics will be calculated to outline the characteristics of the study sample. Normality of data will be assessed using histograms and box plots, while further analysis of skewness and kurtosis will be conducted if normality is not clear from the histograms and box plots. Depending on the distribution of data, participant characteristics will be reported as mean (SD) or median (IQR) and number (percentage) for continuous variables and for categorical variables respectively.

For part A of the study, data will be checked for parametric assumptions. Independent samples t-tests will be used to analyse differences in continuous variables between study groups (obese men with NAFLD and obese men with NAFLD and T2DM in part A of the study). To examine factors associated with NAFLD and T2DM, univariate logistic regression models will be performed with NAFLD and T2DM (diabetic individuals with NAFLD vs. non-diabetic individuals with NAFLD) as the dependent variable. All variables significantly associated with NAFLD and T2DM in univariate logistic regression analyses will be included in multivariate logistic regression analysis.

For part B of the study, baseline descriptive statistics will be summarised by treatment arm (Intervention vs control). Data will be checked for parametric assumptions. For the primary outcome, change in hepatic saturated lipid index (%) from baseline to six weeks due to moderate-intensity exercise training in men with NAFLD and T2DM/prediabetes, treatment arms will be compared using linear regression modelling. The analysis will include a binary indicator for randomisation group as the explanatory variable, terms for the stratification category (ethnicity) and adjustments for the baseline measure of the outcome (hepatic saturated lipid index).

Complete case analysis will be utilised for the primary analysis. Intention to treat will be carried out as sensitivity analysis, using multiple imputation for missing values. Secondary outcomes will be analysed using similar methods as the main analysis, with an appropriate model selected dependent on the distribution of the outcome.

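### The 85% attendance rule removes men from the exercise arm only, so the primary Part B comparison is no longer between the groups as randomised

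*Protocol*

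**What the plan says.** Under its heading on missing and spurious data, Section 14 of the protocol states: "In Part B, participants completing less than 85% of all training sessions will not be included in the final analysis". The sentence does not confine the rule to a secondary or per-protocol analysis.

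Earlier in Section 14, under the statistical methods, the analysis sets for Part B are given as "Complete case analysis will be utilised for the primary analysis" and "Intention to treat will be carried out as sensitivity analysis, using multiple imputation for missing values". The primary model is a linear regression on randomised group, adjusted for ethnicity and for the baseline saturated lipid index. The missing-data paragraph then adds "Missing data will be replaced using multiple imputation or another appropriate method", without saying which analysis this refers to.

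Sections 11 and 12 show who can meet an attendance criterion. In the exercise arm, "Participants randomised to the exercise training group will complete 24 exercise training sessions". In the other arm, "Participants randomised to control will receive no interventions during the six-week intervention phase". Allocation is 1:1, with 13 men per arm (Section 3). Sections 9 and 11 plan post-intervention visits 3 and 4 for Part B participants, with no condition on attendance at training.

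**The concern.** Randomisation makes the two arms comparable at baseline. The 85% rule then filters one arm on what the men did afterwards and leaves the other arm untouched. Men who keep up four sessions a week may be more motivated, healthier or responding better. If so, the retained exercise men differ from the controls for reasons other than exercise, and a difference in saturated lipid index may partly reflect who attended. Since protocol version 5 only one session a week has to be supervised, so completion rests largely on the participant.

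The rule is not a missing-data rule, although it is placed under that heading. A man who completes 20 sessions and attends visit 3 has an observed primary outcome and is a complete case, yet he is discarded.

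Two ambiguities add to this. It is unclear whether the excluded men also leave the intention-to-treat sensitivity analysis; if they do, that analysis is not intention to treat. It is also unclear whether imputation belongs only to the sensitivity analysis or to the analyses generally. Two analysts following Section 14 could report different primary results.

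**Working it through.** **Whom the rule removes.** The exercise arm has 24 sessions and the control arm none. Applied literally to every Part B participant, the rule would exclude all controls (0 of 24), so the only workable reading is that it applies to exercise men alone. The threshold is 0.85 × 24 = 20.4. Since 20/24 = 83.3% fails and 21/24 = 87.5% passes, a man is removed once he misses four sessions, the equivalent of one training week.

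**The protocol's sample size.** The inputs are difference 0.5, SD 0.4, alpha 5% and power 80%. They are stated for Part A, and Part B is said to rest on the same data. Two-sided testing is assumed.

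- Normal approximation: n per arm = 2 × (1.96 + 0.84)² × 0.4² / 0.5² ≈ 10.05, so 11.
- Noncentral t: 11.09, so 12 per arm. This reproduces the stated 24.
- Inflation for 10% drop-out: 24/0.9 = 26.7 and 24 × 1.1 = 26.4, against the stated 26. The allowance is two men in total and is described as being for drop-out only.

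**How many men the rule might remove.** The protocol gives no attendance rate. If each session is attended independently with the assumed probability p, the expected number excluded is 13 × (1 − P(at least 21 of 24)):

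| Assumed p | P(at least 21 of 24) | Expected exclusions of 13 |
|---|---|---|
| 0.95 | 0.970 | 0.4 |
| 0.90 | 0.786 | 2.8 |
| 0.85 | 0.505 | 6.4 |
| 0.80 | 0.264 | 9.6 |

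**Bias and type I error.** The simulation had no true effect, 13 men per arm, SD 0.4 and 20,000 replicates. The k least adherent exercise men were removed and the arms compared by an unadjusted two-sample t-test. The correlation r between adherence and outcome is an assumption.

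| r | k = 2: shift, type I error | k = 3: shift, type I error | k = 4: shift, type I error |
|---|---|---|---|
| 0 | 0.00, 5.0% | not run | 0.00, 5.1% |
| 0.3 | 0.030, 5.2% | 0.045, 5.8% | 0.056, 6.1% |
| 0.5 | 0.053, 6.4% | 0.074, 7.3% | 0.097, 8.7% |
| 0.7 | 0.073, 7.8% | not run | 0.132, 11.8% |

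Against the 0.5 target, 0.045 is 9%, 0.074 is 15% and 0.132 is 26%.

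**Power.** Noncentral t with standardised difference 0.5/0.4 = 1.25:

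| Exercise men analysed | Power, 13 controls | Power, 12 controls |
|---|---|---|
| 13 | 86.4% | 84.8% |
| 12 | 84.8% | 83.3% |
| 11 | 83.0% | 81.5% |
| 10 | 80.9% | 79.3% |
| 9 | 78.3% | 76.7% |
| 8 | 75.1% | 73.6% |

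**The case against.** The protocol does plan an intention-to-treat sensitivity analysis, and it is natural to read that as bringing the excluded men back. This stands as mitigation: the reach of the 85% rule into that analysis is unclear, not settled. But a sensitivity analysis does not change what the primary result is.

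Some men below 85% will have withdrawn without a post-intervention scan. They are already lost under complete case and are within the drop-out allowance. This also stands: observed data are deleted only for low attenders who return for visit 3.

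The objective in Section 8 concerns the impact of six weeks of exercise training, which could be read as a question about efficacy when the training is done. Even so, dropping low attenders from one arm is not a sound way to estimate that effect, because the controls who would have attended poorly stay in.

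The size of the bias rests on assumed correlations and exclusion counts. At r = 0.1 with three men removed the shift is 0.016 and type I error 5.0%. The simulation also omits the planned adjustment for baseline and ethnicity, which could absorb selection acting through those variables. The figures are therefore illustrations.

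Power is a weak argument: with all 13 controls it falls below 80% only when four exercise men are removed. Finally, the imputation sentence may simply describe the method for the sensitivity analysis, so the missing-data wording is better called ambiguous than contradictory.

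**Conclusion.** The concern holds. As written, the primary Part B comparison excludes men on post-randomisation behaviour in one arm only, and intention to treat is relegated to a sensitivity analysis whose population is itself uncertain. This follows from the text and needs no assumption.

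The size of the distortion cannot be derived from the protocol. It is nil if attendance is unrelated to outcome. Over the simulated grid of two to four exclusions and correlations of 0.3 to 0.7, the spurious difference runs from 0.03 to 0.13 and type I error from about 5% to 12%. The loss of power is secondary and modest unless attendance is poor. Because the rule decides whether a co-primary result is a randomised comparison, it should be corrected before the Part B outcome data are analysed.

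**What to change.** In Section 14:

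1. Define the primary Part B analysis as a comparison by allocated arm, whatever the number of sessions completed, using every observed post-intervention scan in the regression already specified (group, ethnicity, baseline index).
2. State one missing-data rule. For example, use observed outcomes in the primary analysis, with multiple imputation by arm for men without a scan as the sensitivity analysis that covers all randomised men. Say explicitly that no one is removed from either analysis for low attendance.
3. Remove the 85% exclusion from the final analysis and keep it only as a per-protocol sensitivity analysis, labelled as such and reported with the number excluded.

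No extra patients, visits or measurements are needed; if all 26 men are analysed, power at the protocol's inputs is 86.4%. The costs are a protocol amendment, which may count as substantial and need the approvals described in Section 17, and a possibly diluted estimate if attendance is poor. The attendance-restricted estimate would still be reported alongside.
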